## 7.3 Liver safety monitoring

To ensure patient safety and enhance reliability in determining the hepatotoxic potential of an investigational drug, a standardized process for identification, monitoring and evaluation of liver events has to be followed.

The following two categories of abnormalities / adverse events have to be considered during the course of the study (irrespective of whether classified/reported as (S)AE):

- Liver laboratory triggers, which will require repeated assessments of the abnormal laboratory parameter
- Liver events, which will require close observation, follow-up monitoring should be entered into the appropriate CRFs. Please refer to Table 14-1 in Appendix 2 for complete definitions of liver laboratory triggers and liver events.

Every liver laboratory trigger or liver event as defined in Table 14-1 of Appendix 2 should be followed up by the investigator or designated personal at the trial site as summarized below. Detailed information is outlined in Table 14-2 in Appendix 2.

For the liver laboratory trigger:

• Repeating the liver function test (LFT) within the next week to confirm elevation.

These LFT repeats must be performed using the central laboratory if possible. If this is not possible, then the repeats can be performed at a local laboratory to monitor the safety of the patient. Repeats laboratory must then be performed at central laboratory as soon as possible. If a liver event is subsequently reported, any local LFTs previously conducted that are associated with this event must be reported on the appropriate CRFs.

• If the elevation is confirmed, close observation of the patient will be initiated, including consideration of treatment interruption if deemed appropriate.

For the liver events:

- Repeating the LFT to confirm elevation as appropriate
- Discontinuation of the investigational drug if appropriate
- Hospitalization of the patient if appropriate
- A causality assessment of the liver event via exclusion of alternative causes (eg, disease, co-medications)
- An investigation of the liver event which needs to be followed until resolution.

These investigations can include serology tests, imaging and pathology assessments, hepatologist's consultancy, based on investigator's discretion. All follow-up information, and the procedures performed must be recorded on the appropriate CRFs.

#### 7.4 Reporting of study treatment errors including misuse/abuse

Medication errors are unintentional errors in the prescribing, dispensing, administration or monitoring of a medicine while under the control of a healthcare professional, patient or consumer (European Medicines Agency (EMA) definition).

Misuse refers to situations where the medicinal product is intentionally and inappropriately used not in accordance with the protocol.

Abuse corresponds to the persistent or sporadic, intentional excessive use of a medicinal product, which is accompanied by harmful physical or psychological effects.

Study treatment errors and uses outside of what is foreseen in the protocol will be collected in the appropriate CRF irrespective of whether or not associated with an AE/SAE and reported to Safety only if associated with an SAE. Misuse or abuse will be collected and reported in the safety database irrespective of it being associated with an AE/SAE.

Table 7-1 Guidance for capturing the study treatment errors including misuse/abuse						
Treatment error type	Document in Dose Administration CRF (Yes/No)	Document in AE CRF	Complete SAE form			
Unintentional study treatment error	Yes	Only if associated with an AE	Only if associated with an SAE			
Misuse/Abuse	Yes	Yes,	Yes, even if not associated with a SAE			

### 7.5 **Prospective suicidality assessment**

The C-SSRS is a questionnaire that prospectively assesses Suicidal Ideation and Suicidal Behavior. The C-SSRS must be administered at each visit, including unscheduled visits.

A validated version of the C-SSRS will be used to capture self-reported C-SSRS data via a web-based interactive response system (eC-SSRS). The eC-SSRS uses a detailed branched logic algorithm to perform the C-SSRS patient interview, evaluating each patient's suicidality ideation and behavior in a consistent manner. At the conclusion of each assessment, the investigator will receive a detailed eC-SSRS Findings Report via e-mail or fax. If the system assesses the patient as having positive suicidal signs, the investigator will be immediately notified by either fax, email and/or via telephone.

If, at any time after screening and/or baseline, the score is "yes" on item 4 or item 5 of the Suicidal Ideation section of the C-SSRS or "yes" on any item of the Suicidal Behavior section, the patient must be referred to a mental health care professional for further assessment and/or treatment. The decision on whether the study treatment should be discontinued is to be taken by the investigator in consultation with the mental health professional to whom the patient is referred.

In addition, all life-threatening events must be reported as SAEs. For example, if a patient answers "yes" to one of the questions in the Suicidal Behavior section, an SAE must be reported if the event was life-threatening. All events of "Non-Suicidal Self-Injurious Behavior" (question also included in the Suicidal Behavior section) should be reported as AEs and assigned the appropriate severity grade.

All SAEs relating to suicidal behavior must be reviewed by the Safety Management Team.

## 7.6 Pregnancy reporting

To ensure patient safety, each pregnancy occurring after signing the informed consent must be reported to Novartis within 24 hours of learning of its occurrence. The pregnancy should be followed up to determine outcome, including spontaneous or voluntary termination, details of the birth, and the presence or absence of any birth defects, congenital abnormalities, or maternal and/or newborn complications. There will be a follow-up of the newborn assessed at approximately 12 months after birth.

The pregnancy must be recorded on the Pharmacovigilance Pregnancy Form and reported by the investigator to the local Novartis Drug Safety and Epidemiology Department. Pregnancy

follow-up should be recorded on the same form and should include an assessment of the possible relationship to the study treatment.

Any SAE experienced during the pregnancy and unrelated to the pregnancy must be reported on a SAE form.

## 8 Data review and database management

#### 8.1 Site monitoring

Before study initiation, at a site initiation visit or at an investigator's meeting, a Novartis representative will review the protocol and data capture requirements with the investigators and their staff. During the study, Novartis employs several methods of ensuring protocol and GCP compliance and the quality/integrity of the sites' data. The field monitor will visit the site to check the completeness of patient records, the accuracy of data capture / data entry, the adherence to the protocol and to Good Clinical Practice, the progress of enrollment, and to ensure that study treatment is being stored, dispensed, and accounted for according to specifications. Key study personnel must be available to assist the field monitor during these visits. Continuous remote monitoring of each site's data may be performed by a centralized Novartis CRA organization. Additionally, a central analytics organization may analyze data & identify risks & trends for site operational parameters, and provide reports to Novartis Clinical Teams to assist with trial oversight.

The investigator must maintain source documents for each patient in the study, consisting of case and visit notes (hospital or clinic medical records) containing demographic and medical information, laboratory data, electrocardiograms, and the results of any other tests or assessments. All information on CRFs must be traceable to these source documents in the patient's file. The investigator must also keep the original informed consent form signed by the patient (a signed copy is given to the patient). The investigator must give the monitor access to all relevant source documents to confirm their consistency with the data capture and/or data entry. Novartis monitoring standards require full verification for the presence of informed consent, adherence to the inclusion/exclusion criteria, documentation of SAEs, and of data that will be used for all primary variables. Additional checks of the consistency of the source data with the CRFs are performed according to the study-specific monitoring plan. No information in source documents about the identity of the patients/subjects will be disclosed.

#### 8.2 Data collection

Designated investigator staff will enter the data required by the protocol into the CRFs using fully validated secure web-enabled software that conforms to US CFR 21 Part 11 requirements. Designated investigator site staff will not be given access to the system until they have been trained.

Automatic validation procedures within the system check for data discrepancies during and after data entry and, by generating appropriate error messages, allow the data to be confirmed or corrected online by the designated investigator site staff. The Investigator must certify that the data entered into the electronic Case Report Forms are complete and accurate. After

database lock or when a site is closed, the investigator will receive copies of the patient data for archiving at the investigational site.

The Principal Investigator is responsible for assuring that the data entered by the site personnel into CRF is complete, accurate, and that entry and updates are performed in a timely manner.

#### 8.3 Database management and quality control

Novartis personnel will review the data entered by investigational staff for completeness and accuracy. Electronic data queries stating the nature of the problem and requesting clarification will be created for discrepancies and missing values and sent to the investigational site via the EDC system. Designated investigator site staff is required to respond promptly to queries and to make any necessary changes to the data.

Concomitant medications entered into the database will be coded using the WHO Drug Reference List, which employs the Anatomical Therapeutic Chemical classification system. Concomitant procedures, non-drug therapies and adverse events will be coded using the Medical dictionary for regulatory activities (MedDRA) terminology.

Laboratory samples will be processed centrally and the results will be sent electronically to Novartis.

ECG readings will be processed centrally and the results will be sent electronically to Novartis.

Diary data will be entered into an electronic diary by the patient OR Patients/subjects will fill in their PRO data in a site based tablet. The system will be supplied by a vendor(s), who will also manage the database. The database will be sent electronically to Novartis.

Randomization codes and data about all study drug(s) dispensed to the patient and all dosage changes will be tracked using an Interactive Response Technology (IRT). The system will be supplied by a vendor, who will also manage the database. The data will be sent electronically to Novartis.

Each occurrence of a code break via IRT will be reported to the clinical team and monitor. The code break functionality will remain available until study shut down or upon request of Novartis.

The occurrence of relevant protocol deviations will be determined. After these actions have been completed and the database has been declared to be complete and accurate, it will be locked and the treatment codes will be unblinded and made available for data analysis. Any changes to the database after that time can only be made after written agreement by Novartis Development management. 8.4 Data Monitoring Committee

Not required.

#### 8.5 Adjudication Committee

Not required.

# 9 Data analysis

The primary analysis will be conducted on all subject data after LPLV (the last Follow-Up Visit) has occurred. Any data analysis carried out independently by the investigator should be submitted to Novartis before publication or presentation.

#### 9.1 Analysis sets

The All Randomized Set (ARS) includes all subjects who were randomized in the study. Subjects will be analyzed according to their randomized treatment, regardless of the treatment received. Tabulations of demographic and baseline characteristics, disposition, and important protocol deviations (IPD) will utilize this analysis set.

The Full analysis set (FAS), which is a subset of ARS, will consist of all participants who started study medication and have completed at least one post-baseline efficacy measurement during the DBTP. In FAS, subjects will be analyzed according to randomized treatment, regardless of the actual treatment received.

The Safety analysis set (SAF) will consist of all randomized subjects who received at least one dose of investigational product and will be analyzed based on actual treatment received.

#### 9.2 Patient demographics and other baseline characteristics

Demographic variables and other baseline characteristics including previous migraine treatments will be summarized. Descriptive statistics (mean, median, standard deviation, minimum, and maximum) will be presented for continuous variables for each treatment group and for all participants (total). The number and percentage of participants in each category will be presented for categorical variables for each treatment group and all participants (total). In addition, all relevant medical history will be summarized following the same strategy.

#### 9.3 Treatments

A data listing and a summary of the investigational drug (AMG 334 or placebo) injections administered will be provided. In addition, the number and percentage of participants receiving rescue medications, concomitant medications, and significant non-drug therapy will be summarized by preferred term (coded by WHO Anatomic Therapeutic Chemical classification [ATC]) and by treatment arm, and be listed.

## 9.4 Analysis of the primary variable(s)

#### 9.4.1 **Primary Variable(s)**

The primary efficacy variable is the change from baseline in monthly migraine days in the last month (Month 3) of the DBTP.

#### 9.4.2 Statistical model, hypothesis, and method of analysis

The primary efficacy endpoint variable will be analyzed using a generalized linear mixed model based on observed monthly data during the DBTP and pairwise comparisons (AMG 334 140mg vs. placebo, and AMG 334 70mg vs. placebo) will be conducted.

The model will include treatment, scheduled visit, treatment by visit interaction, and the stratification variable and baseline values as covariates. If applicable, unstructured covariance structure is assumed. Least squares means (LSMs) for each treatment group and its associated 95% confidence intervals, difference of LSMs compared to placebo group and the associated 95% confidence interval of the differences, as well as the nominal two-sided p-values, will be tabulated by visit and treatment.

A hierarchical gate-keeping procedure and the Hochberg method will be used to maintain the overall 2-sided study-wise type I error rate at 0.05 for the primary endpoint and secondary efficacy endpoints. See further details in Section 9.5.

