## 9.5 Analysis of secondary variables

#### 9.5.1 Efficacy variables

The secondary efficacy variables (all during the DBTP) are:

- Proportion of patients who achieve at least a 50% reduction from baseline in monthly migraine days in the last month of DBTP (Month 3).
- Change from baseline in monthly acute migraine-specific treatment days in Month 3 of the DBTP
- Change from baseline in headache impact scores as measured by the HIT-6 in Month 3 of the DBTP

The above continuous endpoints (ie, change from baseline) will be analyzed using a linear mixed effects model similar to the primary endpoint. The dichotomous endpoints will be analyzed by Cochran-Mantel-Haenszel (CMH) test with patients who are missing monthly migraine day data at Month 3 of the DBTP imputed as non-responders. Nominal 95% confidence intervals and p-values will be reported.

A hierarchical gate-keeping procedure and the Hochberg method will be used to maintain the overall 2-sided study-wise type I error rate at 0.05 for the primary endpoint and secondary efficacy endpoints. The primary endpoint, the change from baseline in monthly migraine days to the last 4 weeks of the 12-week double-blind treatment period, will be initially tested at a 2-sided significance level of 0.025 for each of the AMG 334 treatment group (140 mg and 70 mg) compared to the placebo group, respectively. If the primary endpoint and all secondary endpoints are statistically significant for an AMG 334 treatment group, the corresponding significance level will be carried over to the primary endpoint for the other AMG 334 treatment group, and the primary endpoint will be re-compared to the placebo group at a 2-sided significance level of 0.05 (full alpha). If the primary endpoint of one dose group is statistically significant but not all the secondary endpoints, only half of the initial alpha of the dose (0.0125) can be transferred to the primary endpoint of the other dose. The testing sequence can be found in the figure below.

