#### 9.8 Sample size calculation

A treatment difference of -1.79 days for change from baseline in monthly migraine days in Month 3 between AMG 334 140mg and placebo was observed in study 20120296 (STRIVE). A treatment difference of -1.16 days for change from baseline in monthly migraine days in Month 3 between AMG 334 70mg and placebo was observed based on pooled analysis on the combined data from studies 20120296, 20120297, and 20120178.

Assuming a treatment effect similar to the effect observed in previous studies with AMG 334 in episodic migraine, the treatment difference in terms of change from baseline on monthly migraine days during week 9-12 (primary variable) for erenumab 140mg vs. placebo and 70mg vs. placebo is assumed at -1.5 days and -1.1 days, respectively. The common standard deviation of the primary variable is assumed at 4. Given a 2:3:3 randomization ratio among erenumab 140mg, 70mg, and placebo, a total of 880 subjects (including 10% drop out rate) would enable both doses to achieve higher than 90% power under overall 0.05 full alpha level to detect the designed treatment difference. In addition, the sample size will also ensure the trial to have adequate power to detect treatment difference under initial 2-sided 0.025 alpha level assigned to each dose (equally split between the erenumab two doses).

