2.6.2 Statistical hypothesis, model, and method of analysis

Analysis of secondary efficacy endpoints will utilize the FAS except for the analysis of change from baseline in monthly acute migraine-specific treatment days in Month 3 of the DBTP, which will be conducted based on the subgroup of patients who used acute migraine-specific medication during baseline. Subjects will be analyzed according to their randomized treatment group regardless of the actual treatment received during the study.

The above continuous change from baseline efficacy endpoints will be analyzed using a linear mixed effects repeated measures model with treatment group, baseline value, stratification factor, scheduled visit, and the interaction of treatment group with scheduled visit, without any imputation for missing data. If applicable, in the repeated statement, an unstructured covariance matrix will be used.

The dichotomous endpoint (Proportion of patients who achieve at least a 50% reduction from baseline in monthly migraine days in the last month of DBTP) will be analyzed based on Cochran-Mantel-Haenszel (CMH) test after patients who have missing monthly migraine day data at Month 3 of the DBTP imputed as non-responders.

The description of the models can be found in Section 5.4.

In all cases, estimates (difference or odds ratio) of treatment group compared to placebo group with associated nominal 95% confidence intervals and nominal two-sided p-values will be provided.

A hierarchical gate-keeping procedure and the Hochberg method will be used to maintain the overall 2-sided study-wise type I error rate at 0.05 for the primary endpoint and secondary efficacy endpoints. The primary endpoint, the change from baseline in monthly migraine days

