5.4 Statistical models

5.4.1 **Primary analysis**

The primary endpoints of the study will be first tested for each of AMG 334 70 mg and 140 mg compared to placebo, respectively.

- Null Hypothesis: In subject with episodic migraine, the AMG 334 treatment group is the same as placebo, in terms of the reduction from baseline in mean monthly migraine days in the last month (month 3) of the DBTP
- Alternative Hypothesis : In subject with episodic migraine, the AMG 334 treatment group is different from placebo, in terms of the reduction from baseline in mean monthly migraine days in the last month (month 3) of the DBTP

It will be analyzed using a linear mixed effects repeated measures model with treatment group, baseline value, stratification factor, scheduled visit, and the interaction of treatment group with scheduled visit. In repeated statement, an unstructured covariance matrix will be used.

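### The repeated-measures models share one baseline slope across Months 1 to 3 although only Month 3 is tested; adding baseline-by-visit is a small, nearly free improvement

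*Protocol*

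**What the plan says.** The primary variable is the "change from baseline in monthly migraine days in the last month (Month 3) of the DBTP". Protocol 9.4.2 gives the model: "The model will include treatment, scheduled visit, treatment by visit interaction, and the stratification variable and baseline values as covariates". On the covariance it says, where applicable, that "unstructured covariance structure is assumed".

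SAP 2.5.2 repeats this. SAP 5.4.1 lists treatment group together with "baseline value, stratification factor, scheduled visit, and the interaction of treatment group with scheduled visit". For the continuous secondary endpoints, HIT-6 and acute migraine-specific medication days, SAP 2.6.2 specifies a "linear mixed effects repeated measures model with treatment group, baseline value, stratification factor, scheduled visit, and the interaction of treatment group with scheduled visit". Table 2-4 and SAP 5.4.2.2 have the same terms, and Protocol 9.5.1 refers back to the primary model. None of these places lists a baseline-by-visit interaction.

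Each dose is "initially tested at a 2-sided significance level of 0.025" against placebo. LS means and nominal p-values are tabulated at every visit, but the hypotheses in SAP 2.5.2, 5.4.1 and 5.4.2.2 concern Month 3 only.

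The sensitivity analyses of the primary endpoint are built differently. SAP 2.5.4 uses a Week 12 ANCOVA with baseline as covariate. SAP 5.1.5.3.2 allows the multiply imputed data to be analysed at Week 12 alone. Both therefore estimate a baseline slope specific to Month 3.

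**The concern.** The response is a change score, so its slope on baseline equals the slope of the monthly value on baseline, minus 1. If the monthly value tracks baseline less closely as time passes, the change-score slope becomes steeper from Month 1 to Month 3. A single slope then under-adjusts Month 3. With an unstructured covariance, the common slope is a generalised least squares average over months, and Month 3 need not carry much of the weight.

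Two things follow, each under its own condition:

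- **Precision.** If slopes differ by month, the unexplained part enters the Month 3 residual variance.
- **Bias.** The primary analysis uses observed data without imputation. If slopes differ by month and dropout is also related to baseline differently in the arms, the arms' Month 3 means are adjusted with the wrong slope and the difference shifts.

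There is also a point of interpretation. The primary model and its Week 12 sensitivity analyses differ in baseline adjustment as well as in missing-data handling. A gap between them could not be attributed to missing data alone.

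**Working it through.** **1. The plan's own power.** Protocol 9.8 gives the differences "for erenumab 140mg vs. placebo and 70mg vs. placebo is assumed at -1.5 days and -1.1 days, respectively", with SD 4, 880 patients at 2:3:3 and 10% dropout. SAP 1.1 gives arms of 330, 330 and 220, which leaves 297, 297 and 198 after dropout. Power = Φ(|δ|/SE − z), with SE = 4·√(1/n₁ + 1/n₀).

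- 70 mg: SE = 4·√(2/297) = 0.328 and 1.1/SE = 3.351. Power is 91.8% at 0.05 and 86.6% at 0.025.
- 140 mg: SE = 4·√(1/198 + 1/297) = 0.367 and 1.5/SE = 4.087. Power is 98.3% at 0.05 and 96.8% at 0.025.

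The claim of more than 90% at 0.05 reproduces for both doses.

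**2. Assumptions for sizing the concern.** The documents give no slopes, month-specific SDs, correlations, baseline SD or dropout mechanism. Assumed here: baseline SD 2.7 within the 4-14 day entry range, Month 3 residual SD 3.8, equal correlations of 0.65, and either equal SDs or SDs rising as 3.2/3.6/3.8.

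**3. Weights in the common slope.** With complete data, w = V⁻¹1/(1ᵀV⁻¹1).

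- Equal SDs: 0.33/0.33/0.33.
- Rising SDs: 0.58/0.27/0.15. The Month 3 weight falls from 18% to 7% as the correlation rises from 0.60 to 0.75.

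**4. Loss of precision.** Inflation of the Month 3 variance = (Month 3 slope − pooled slope)² × 2.7² / 3.8², with 2.7² = 7.29 and 3.8² = 14.44.

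| Slopes, Months 1/2/3 | SDs | Pooled slope | Gap | Inflation |
|---|---|---|---|---|
| equal | any | same | 0 | 0% |
| -0.3/-0.4/-0.5 | equal | -0.400 | 0.100 | 0.073/14.44 = 0.5% |
| -0.3/-0.4/-0.5 | rising | -0.357 | 0.143 | 0.149/14.44 = 1.0% |
| -0.2/-0.4/-0.6 | equal | -0.400 | 0.200 | 0.292/14.44 = 2.0% |
| -0.2/-0.4/-0.6 | rising | -0.314 | 0.286 | 0.598/14.44 = 4.1% |

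At correlation 0.75 with rising SDs (weights 0.69/0.24/0.07), the steeper slopes give a pooled slope of -0.277, a gap of 0.323 and 5.3%.

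**5. Effect on power.** For the 4.1% row, √1.041 = 1.020 and 3.351 × 1.020 = 3.419. If the planning SD of 4 is taken as what the common-slope model attains, 70 mg power would rise with the interaction from 91.8% to Φ(3.419 − 1.960) = 92.8% at 0.05. At 0.025 it would rise from 86.6% to Φ(3.419 − 2.241) = 88.1%.

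A separate large-sample fit compared both models on the same data, with baseline SD about 2.5 and correlation 0.6 or 0.8. It gave smaller gains: about 0.2% of the SE for -0.3/-0.4/-0.5 and 0.5-0.9% for -0.1/-0.3/-0.5. Power at 0.05 was then 91.9% and 92.2%.

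**6. Bias at about 10% dropout.**

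- Dropout related to baseline equally in all arms: about 0.
- Dropout related to baseline in placebo only (simulation, 330 per arm, true difference -1.10, rising SDs): mean -1.14 with slopes -0.3/-0.4/-0.5 and -1.18 with -0.2/-0.4/-0.6. That is 0.04 and 0.08 day.
- Dropout related to baseline in opposite directions on active and placebo (log-odds 1 per baseline SD): about 0.06 day for -0.3/-0.4/-0.5 and 0.11-0.13 day for -0.1/-0.3/-0.5.
- Stress case, slopes 0/-0.3/-0.7 with the same opposite dropout: about 0.2 day.

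All these shifts enlarged the apparent benefit because of the dropout direction simulated; reversing that direction would reverse the sign.

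**The case against.** The strongest reply is that this is an efficiency refinement of negligible size. Without dropout, randomisation keeps the common-slope contrast unbiased. With equal slopes nothing is lost. The larger precision figures need both a slope that triples over three months and SDs that rise, and the documents support neither. All of that stands, and it is why the point is minor.

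A reader might infer that baseline-related dropout alone biases the result. It does not. The dependence must differ by arm and the slopes must differ by month. A reader might also infer that the >90% power claim fails. It does not: the 91.8% and 98.3% in the working are computed from the plan's own SD of 4.

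The plan also has safeguards. The Week 12 ANCOVA and the Week 12 analysis of the imputed data use a Month 3 slope for the primary endpoint. SAP 5.1.5.3 calls for further examination if missingness is high or unbalanced. Protocol 5.6.2 keeps patients recording in the eDiary after stopping treatment. SAP 5.1.5.1 sets a month to missing only with fewer than 14 diary days. Protocol 3.6 reports about 95% retention on active at three months in earlier trials.

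These safeguards limit the damage for the primary endpoint but do not argue against the term. Cover is thinner for the continuous secondary endpoints: Table 2-4 lists no sensitivity analysis for them, although SAP 5.1.5.3 speaks of primary and secondary endpoints. On the other hand, nothing was computed here for HIT-6 or medication days, so for those the case rests on the shared model form alone.

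**Conclusion.** The point holds as a minor, conditional one. Every statement of the model gives a single baseline slope for three months when only the last is tested. The cost in squared standard error is 0% with equal slopes, about 0.5-1% with slopes -0.3/-0.4/-0.5, and about 2-4% with -0.2/-0.4/-0.6 (correlation 0.65, baseline SD 2.7, equal to rising SDs). Bias at about 10% dropout is roughly 0.04-0.12 day against assumed effects of 1.1 and 1.5 days, and only if slopes differ by month and baseline-related dropout differs by arm; otherwise it is about zero. All these sizes rest on assumed inputs. Neither the stated power at 0.05 nor the validity of the primary test under randomisation is in question.

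**What to change.** Add the baseline-by-visit interaction to the repeated-measures model for change in monthly migraine days, and likewise for HIT-6 and acute migraine-specific medication days. The places to change are Protocol 9.4.2 and 9.5.1 and SAP 2.5.2, 2.6.2, Table 2-4, 5.4.1 and 5.4.2.2. Specify it before the treatment codes are opened.

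The cost is 2 degrees of freedom per model, with no new data and no change to hypotheses or alpha. The term is not free in every case: with equal slopes and dropout in opposite directions by arm, the Month 3 standard error was 0.1-0.2% larger with it at 10% dropout. The baseline value at which LS means are evaluated needs no special rule for the contrast, because the model has no treatment-by-baseline term. As a side benefit, the primary model and the Week 12 sensitivity analyses would then both use a Month 3 baseline slope.
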